8.2 Baseline Measures

For each subject, the baseline value of a parameter is defined as the last assessment of that parameter on or prior to the date/time of the first dose of the double-blind study medication.

If time of measurement of a parameter or time of first dose are missing, then the baseline value is defined as the last assessment of that parameter on or prior to the date of the first dose of the double-blind study medication.

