6 STUDY PERIODS, TREATMENT REGIMENS AND POPULATIONS FOR ANALYSES

6.1 Study Periods

In this study, there are five study periods: Screening period, Double-Blind Period, Open-Label Period, Cumulative Abatacept Period and Follow-up Period. The following analysis periods defined below are for analysis purposes. The definitions below indicate the data to be included in the analysis of each specified period.

- **Screening period:** It covers the time period which starts from the day of enrollment and lasts until the initiation of the randomized Double-Blind Period.
- **Double-Blind Treatment Period:** It starts at the time of the first dose of blinded treatment and continues up to 56 days post last dose in the Double-Blind Period or prior to the first dose in the open-label period, whichever is earlier for safety (AE and laboratory summaries). Up to 42 days post last dose in the Double-Blind Period or prior to the first dose in the open-label period, whichever is earlier for efficacy analyses. Up to 21 days post last dose in the Double-Blind Period or prior to the first dose in the open-label period, whichever is earlier for on-treatment immunogenicity summaries.
- **Open-Label period:** It starts at the time of the first dose of open-label treatment and continues up to 56 days post last dose for safety (AE and laboratory summaries). Up to 42 days post last dose for efficacy analyses and up to 21 days post last dose for the on-treatment immunogenicity summaries.
- **Cumulative Abatacept Period:** It starts at the time of the first dose of abatacept (either in the Double-Blind Period for the subjects randomized to abatacept or in the open-label period for the subjects randomized to placebo) and continues up to 56 days post last dose of abatacept for safety (AE and laboratory summaries) and up to 21 days post last abatacept dose for the on-treatment immunogenicity summaries. The last abatacept dose can be last dose in Double-Blind Period for subjects not treated in the open-label period.
- **Follow-up Period:** immunogenicity summaries are provided for the follow-up period that starts at Day 22 post last dose and continues up to last assessment of immunogenicity in the study.

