7.4 Extent of Exposure

7.4.1 Study Therapy

The extent of exposure during the double-blind (for the As-treated Analysis Population) and the cumulative abatacept periods (for the cumulative abatacept population) will be summarized in the following ways:

- Number of abatacept/placebo injections
- Number of days a subject is known to be on study drug.

The number of injections subjects received will be based on the study medication page of the CRF when it is indicated that a subject received the study medication.

The number of days the subject is known to be on study drug (exposure to study drug) during the Double-Blind Period is calculated as:

For subjects who discontinued during the Double-Blind Period OR completed the Double-Blind Period but not treated in open-label period OR not treated in the open-label period within 56 days of the last injection in the Double-Blind Period:

Exposure in days = (date of last injection in the Double-Blind Period - date of first injection in the Double-Blind Period + 1) + 56.

For subjects who were treated in the open-label within 56 days of the last injection of the Double-Blind Period:

Exposure in days = (date of first injection in the open-label period - date of first injection in the Double-Blind Period).

Exposure in cumulative abatacept period for subjects who discontinued treatment in double-blind or open-label OR who completed double-blind and not treated in Open-label or who completed open-label is calculated as:

Exposure in days = (date of last abatacept injection - date of first abatacept injection + 1) + 56

In case a patient randomized to abatacept does not go into open-label within 56 days post last dose in double-blind, the exposure has to be adjusted for the gap exceeding 56 days.

Exposure in cumulative abatacept period for subjects who are on-going in open-label period is calculated as:

Exposure in days = cut-off date - date of first abatacept injection with cut-off date = the date database lock date.

For subjects randomized to placebo, the date of first abatacept injection is date of first open-label abatacept treatment. For subjects randomized to abatacept, the date of first abatacept injection is the date of first double-blind abatacept treatment.

The date of last abatacept injection can be the last date of abatacept in double-blind if the subject is not treated in open-label or the date of last abatacept injection in open-label if subject is treated in open-label.

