7.6.3 Laboratory Evaluation

Unless otherwise specified, laboratory data obtained after the start of study medication dosing up to the first dose in the open-label period or up to and including 56 days after the last double-blind dosing date, whichever occurs first will be considered as obtained during Double-Blind Treatment Period. For the cumulative abatacept period, laboratory data obtained after the start of abatacept up to and including 56 days after the last abatacept dose will be considered as obtained during the cumulative abatacept period.

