7.6.3.2 Change from Baseline for Selected Laboratory Parameters

Scheduled laboratory measurements and corresponding change from baseline values will be summarized (mean baseline with standard deviation, mean post-baseline with standard deviation, mean change from baseline with standard error and 95% CI for change from baseline) by time point and laboratory test. For the Double-Blind Treatment Period (As-Treated Analysis Population) summaries will be provided by treatment group. For the cumulative abatacept period (cumulative abatacept population) all subjects' data will be combined into one treatment group.

Visit windows are provided in [Section 8.5](#) in order to link each laboratory test to a scheduled visit. The following laboratory parameters will be analyzed:

- Hemoglobin
- Hematocrit
- Total leukocyte
- Basophils
- Eosinophils
- Lymphocytes
- Monocytes
- Neutrophils
- Platelet count
- Aspartate aminotransferase (AST)
- Alanine aminotransferase (ALT)
- Total bilirubin
- Alkaline phosphatase
- Creatinine
- Blood Urea Nitrogen (BUN)
- Bicarbonate
- GGT (Gamma-glutamyltransferase)
- Glucose
- Total Protein
- Albumin
- Sodium
- Potassium
- Chloride
- Calcium
- Phosphorus
- Creatine kinase
- hsCRP
- Urine pH

Subjects who have laboratory measures at baseline and corresponding measure at the given on-treatment visit will be included in the laboratory analyte assessment. Note that not all subjects have laboratory determinations for all analytes at all visits, and therefore the sample size may vary from analyte to analyte at each time point. The 95% CI for the change from baseline within the treatment arm will be constructed based on t-test.

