8.5 Day Ranges for Analysis Time Points

Subjects do not always adhere strictly to the visit schedule timing in the protocol. Therefore, the designation of visits during the study period will be based on the day of evaluation relative to the Day 1 of the trial (day of first dosing = study Day 1) rather than the nominal visit recorded in the case report form (CRF). Tables below define visit windows to be used (note that the window for the Day 1 visit contains the first dosing day only). If a subject has more than one visit where a measurement is recorded within a window, the measurement closest to the target day will be used. In case of two visits being equally distant from the target day, the later measurement will be used in analyses. Exception to these rules applies to immunogenicity. For this, the least favorable value (toward a positive response) in the window will be used.

For subjects who discontinue from study therapy prematurely or completed the study, assessments performed after the last dose of study drug will be included in the efficacy data sets provided that the corresponding study visit is made within 42 days of the last dose. For some sensitivity analyses (see [Section 7.1.5](#)) all data available for the subject will be used, regardless of whether the visit is made within 42 days of the last dose.

For subjects who discontinued study drug, only assessments done within 42/56 (efficacy/safety) days after the last dose of study drug would be included for analysis purposes using the visit windows below.

Table 8.5-1: Day Ranges for Safety and Efficacy Analyses

Visit	Target Day	Safety Assessments(Vitals and, Laboratory (Hematology, Chemistry, Urinalysis)), and the following Efficacy Assessments: hsCRP, ESR, PK, ESSDAI, Joints, PhyGAD, SubGAD, ESSPRI, PROMIS Fatigue, Oral and Ocular Dryness	Efficacy Assessments: SF-36, FSFI, Unstimulated/Stimulated Salivary Flow, Schirmer Test, Tear Break-Up Time, Ocular Staining Score
Double-Blind Period*			
Day 1	1	≤ 1	≤ 1
Day 29 (Week 4)	29	2 - 43	
Day 57 (Week 8)	57	44 - 71	
Day 85 (Week 12)	85	72 - 99	2 - 127
Day 113 (Week 16)	113	100 - 127	
Day 141 (Week 20)	141	128 - 155	
Day 169 (Week 24/ET)	169	156 - 183 ^a	128 - 212 ^a
Open-Label Period*			
Day 197 (Week 28)	197	184 ^b - 211	
Day 225 (Week 32)	225	212 - 239	
Day 253 (Week 36)	253	240 - 267	213 ^b - 308
Day 281 (Week 40)	281	268 - 295	
Day 309 (Week 48)	309	296 - 323	
Day 365 (Week 52/ET)	365	324 - 351 ^c	309 - 421 ^c

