* See Section 6.1 for the definition of double-blind and open-label periods

^a The upper limit of the last visit window is 42/56 (efficacy/safety) days post the last study drug dose during the Double-Blind Period or the first dose date in the Open-Label period, whichever is earlier.

^b The lower limit of the first visit window in the open-label period is the day after the first open-label dose.

^c The upper limit of the last visit window is 42/56 (efficacy/safety) days post the last study drug dose during the open-label period.

Table 8.5-2: Day Ranges for Immunogenicity

Visit	Target Day	Day Range
Double-Blind Period*		
Day 1	1	≤ 1
Day 85 (Week 12)	85	2 - 127
Day 169 (Week 24/ET)	169	128 - 267 ^a
Open-Label Period*		
Day 365 (Week 52/ET)	365	268 ^b - 421 ^c

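### Pooled cumulative-abatacept lab changes use the pre-double-blind baseline and trial-day windows, so placebo switchers' change scores span 24 weeks on placebo

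*SAP*

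**What the plan says.** SAP 6.1 begins the Cumulative Abatacept Period at the first abatacept dose: in the double-blind period for subjects randomized to abatacept, "or in the open-label period for the subjects randomized to placebo". SAP 7.6.3 restricts the laboratory values for this period to "laboratory data obtained after the start of abatacept up to and including 56 days after the last abatacept dose". Exposure follows the same anchor: for a placebo subject, 7.4.1 says "the date of first abatacept injection is date of first open-label abatacept treatment".

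SAP 7.6.3.2 then summarises lab values and change from baseline by time point, with a 95% CI for the change. For the cumulative period, all subjects' "data will be combined into one treatment group". It refers to the windows of 8.5 "in order to link each laboratory test to a scheduled visit". SAP 7.6.4 uses the same windows and the same pooling for vital signs, but states no change from baseline.

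Two rules complete the calculation. Baseline in 8.2 is the last assessment "on or prior to the date/time of the first dose of the double-blind study medication", for every subject and parameter. Visits in 8.5 are assigned "based on the day of evaluation relative to the Day 1 of the trial (day of first dosing = study Day 1"). No readable section gives another baseline or time origin for the cumulative period. SAP 7.6 and 8.7 also say that safety data follow sponsor safety conventions, which are not part of the documents.

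**The concern.** The period, the lab values admitted to it and the exposure are all tied to the first abatacept dose. The baseline and the visit axis are not. For a subject who started on abatacept the two anchors coincide. For a placebo switcher they lie 24 weeks apart.

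A table meant to show lab change on abatacept would therefore have open-label rows with two mixtures in them. Change that arose on placebo is added to change on drug. Early on-drug values are averaged with values from subjects treated 24 weeks longer. Because the arms are pooled, a reader cannot separate them. Up to 86 of the 172 planned subjects are concerned, if every placebo subject switches. SAP 9 puts cumulative-period safety data in the Month 6 report and the final safety analysis in the Year 1 report, so both could carry the table.

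**Working it through.** **Inputs.** Double-blind period Day 1 to Day 169, 24 weeks (SAP 2.1). Open-label abatacept from Day 169, weekly to Day 357 (SAP 2.1). Allocation 1:1, 86 per arm (SAP 2.1 and 5). Open-label visit days from Protocol Table 5.1-3. Assumption: open label starts exactly on Day 169.

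**The plan's own figure.** (169 − 1)/7 = 24.0 weeks, as stated.

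**Time on drug.** At trial Day D, days since the 8.2 baseline are D − 1, taking baseline on Day 1. Days on abatacept are D − 1 in the abatacept arm and D − 169 in switchers. The placebo share of a switcher's change interval is 168/(D − 1).

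| Trial day | Abatacept arm, days on drug | Switchers, days on drug | Placebo share of switchers' interval |
|---|---|---|---|
| 197 | 196 | 28 | 168/196 = 86% |
| 225 | 224 | 56 | 168/224 = 75% |
| 253 | 252 | 84 | 168/252 = 67% |
| 281 | 280 | 112 | 168/280 = 60% |
| 309 | 308 | 140 | 168/308 = 55% |
| 337 | 336 | 168 | 168/336 = 50% |
| 365 | 364 | 196 | 168/364 = 46% |

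The difference in days on drug is 168 at every visit. Table 8.5-1 has no Day 337 row and prints 324-351 for Day 365, so Day 365 itself is reached only through the footnote that extends the last window to 42/56 "days post the last study drug dose during the open-label period".

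**Effect on a row mean.** Let A be the abatacept arm's mean change, S the switchers' mean change since first abatacept, d their mean change over the placebo phase, and s the switchers' share of the row.

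- As written: (1 − s)A + s(S + d).
- Same subjects in the row, switchers' baseline moved to first abatacept: (1 − s)A + sS.
- Difference: s × d.

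With continuation rates p (placebo arm) and q (abatacept arm), s = p/(p + q):

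- equal continuation (assumed): s = 0.50, so the shift is 0.50d;
- p = 70%, q = 90% (assumed): 0.70/1.60 = 0.44, so 0.44d;
- p = 90%, q = 70% (assumed): 0.90/1.60 = 0.56, so 0.56d.

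The documents give no value for d. Full re-windowing also moves switchers to other rows, so s × d is not the difference between the table as written and the table as fixed.

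**Whether re-anchoring fits the schedule.** A switcher's abatacept day is D − 168. Trial Days 197, 225, 253, 281, 309, 337 and 365 become 29, 57, 85, 113, 141, 169 and 197, each an existing visit day.

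**The case against.** **The sponsor conventions may already settle this.** SAP 7.6 and 8.7 defer to them, and a period-specific lab baseline could well be there. This cannot be checked and is the main limit on the point. However, 7.6.3.2 sends the reader expressly to the 8.5 windows, and nothing says that a convention overrides 8.2 or 8.5.

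**One study-entry baseline is a legitimate choice in an extension.** It is when the arms are shown separately, as in the Day 1 to Day 365 efficacy analysis of SAP 7.5.2.1, which keeps the randomized treatment in the model and reports each arm. It is harder to defend in one pooled column for a period defined by time since first abatacept.

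**The output carries little weight.** This stands. The table is descriptive, and safety has no testing of group differences. The protocol's laboratory safety endpoint is the proportion with marked abnormalities. The size of the baseline effect is also unknown: if labs do not drift on placebo, that half of the point vanishes and only the mixed time axis remains.

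**The open-label lab rows may be sparse.** The readable schedule does not show the open-label hematology and chemistry visits, so which rows are filled cannot be confirmed. Table 8.5-1 does set open-label windows for these tests. Also, hsCRP, which is on the 7.6.3.2 list, is needed for DAS28-CRP, which is followed to Day 365.

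**Stronger readings that fail.** A reader might infer that samples drawn on placebo are pooled into the abatacept table. They are not: 7.6.3 admits only values after abatacept starts, and it is the change interval that reaches back. A reader might also infer that abnormality or event rates on abatacept are contaminated. The documents do not support this, because those summaries include only results or events from the abatacept period and do not use change from baseline.

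**Conclusion.** The point holds on the readable SAP text and is minor. Applying 7.6.3.2, 8.2 and 8.5 together puts 168 placebo days into each switcher's change score. It also combines times on abatacept 168 days apart in every open-label row. With equal continuation and unchanged row membership, about half of any mean placebo-phase lab change enters the pooled row (0.44 to 0.56 under the assumed unequal rates). For vital signs only the time axis is affected.

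Unaffected are efficacy, adverse events, exposure, marked abnormalities (7.6.3.1) and the by-arm double-blind lab table. Rows up to Day 169 are also unaffected, since under the start-date assumption they hold only the original abatacept arm.

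The conclusion rests on open label starting at Day 169 and on no overriding rule in the sponsor conventions.

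**What to change.** 1. In 8.2, for Cumulative Abatacept Period lab change summaries, define baseline as the last value on or before the first abatacept injection as defined in 7.4.1. Keep the date-only fallback that 8.2 already has for missing times.
2. In 8.5, for cumulative-period labs and vital signs, count windows from that injection as Day 1: 2-43 for Day 29, then 28-day windows from 44-71 (Day 57) to 324-351 (Day 337). The last window, for Day 365, runs from Day 352 to 56 days after the last abatacept dose. The footnotes that split windows at the first open-label dose should not apply to this axis.
3. State openly that Table 8.5-1 lacks a Day 337 row and prints 324-351 for Day 365, and correct this at the same time.
4. If the sponsor conventions already set a period-specific baseline and windows, it is enough to say that they override 8.2 and 8.5 for this period.

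Keep the period definition of 6.1 and 7.6.3. No values need to be excluded for a dosing gap: the gap adjustment in 7.4.1 concerns exposure only.

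**Cost.** SAP wording, one extra baseline flag and one extra visit variable. The anchor date is already derived for exposure. Day 169 assessments precede the injection (Protocol 3.1.3), so a pre-dose value exists wherever the test was done; other switchers use an earlier value.

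**Downsides.** Rows beyond about 28 weeks on abatacept rest mainly on the original abatacept arm. A switcher's last dose falls on abatacept Day 357 − 168 = 189, so switcher values can reach Day 189 + 56 = 245 at most. After a long dosing gap the axis shows time since first abatacept, not time on drug.

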8.3 Missing Measurements

For listings of efficacy measures, missing values will be represented as missing. For analyses involving binary secondary endpoints (the proportion of subjects with a decrease in ESSDAI of at least 3 from baseline and the proportion of subjects with a decrease in the ESSPRI of at least 1) a missing responder value due to discontinuation or for other reasons will be imputed as a non-responder.

8.5 Day Ranges for Analysis Time Points

Subjects do not always adhere strictly to the visit schedule timing in the protocol. Therefore, the designation of visits during the study period will be based on the day of evaluation relative to the Day 1 of the trial (day of first dosing = study Day 1) rather than the nominal visit recorded in the case report form (CRF). Tables below define visit windows to be used (note that the window for the Day 1 visit contains the first dosing day only). If a subject has more than one visit where a measurement is recorded within a window, the measurement closest to the target day will be used. In case of two visits being equally distant from the target day, the later measurement will be used in analyses. Exception to these rules applies to immunogenicity. For this, the least favorable value (toward a positive response) in the window will be used.

For subjects who discontinue from study therapy prematurely or completed the study, assessments performed after the last dose of study drug will be included in the efficacy data sets provided that the corresponding study visit is made within 42 days of the last dose. For some sensitivity analyses (see [Section 7.1.5](#)) all data available for the subject will be used, regardless of whether the visit is made within 42 days of the last dose.

For subjects who discontinued study drug, only assessments done within 42/56 (efficacy/safety) days after the last dose of study drug would be included for analysis purposes using the visit windows below.

Table 8.5-1: Day Ranges for Safety and Efficacy Analyses

Visit	Target Day	Safety Assessments(Vitals and, Laboratory (Hematology, Chemistry, Urinalysis)), and the following Efficacy Assessments: hsCRP, ESR, PK, ESSDAI, Joints, PhyGAD, SubGAD, ESSPRI, PROMIS Fatigue, Oral and Ocular Dryness	Efficacy Assessments: SF-36, FSFI, Unstimulated/Stimulated Salivary Flow, Schirmer Test, Tear Break-Up Time, Ocular Staining Score
Double-Blind Period*			
Day 1	1	≤ 1	≤ 1
Day 29 (Week 4)	29	2 - 43	
Day 57 (Week 8)	57	44 - 71	
Day 85 (Week 12)	85	72 - 99	2 - 127
Day 113 (Week 16)	113	100 - 127	
Day 141 (Week 20)	141	128 - 155	
Day 169 (Week 24/ET)	169	156 - 183 ^a	128 - 212 ^a
Open-Label Period*			
Day 197 (Week 28)	197	184 ^b - 211	
Day 225 (Week 32)	225	212 - 239	
Day 253 (Week 36)	253	240 - 267	213 ^b - 308
Day 281 (Week 40)	281	268 - 295	
Day 309 (Week 48)	309	296 - 323	
Day 365 (Week 52/ET)	365	324 - 351 ^c	309 - 421 ^c

* See Section 6.1 for the definition of double-blind and open-label periods

^a The upper limit of the last visit window is 42/56 (efficacy/safety) days post the last study drug dose during the Double-Blind Period or the first dose date in the Open-Label period, whichever is earlier.

^b The lower limit of the first visit window in the open-label period is the day after the first open-label dose.

^c The upper limit of the last visit window is 42/56 (efficacy/safety) days post the last study drug dose during the open-label period.

Table 8.5-2: Day Ranges for Immunogenicity

Visit	Target Day	Day Range
Double-Blind Period*		
Day 1	1	≤ 1
Day 85 (Week 12)	85	2 - 127
Day 169 (Week 24/ET)	169	128 - 267 ^a
Open-Label Period*		
Day 365 (Week 52/ET)	365	268 ^b - 421 ^c

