Schirmer Test ^c				X				X	
Tear break-up time ^c				X				X	
Ocular staining score ^c				X				X	

Table 5.1-3: Open-Label Treatment Period Procedural Outline (IM101603)^a

Procedure	Day 169 (WK 24) ^b	Day 197 (Wk 28)	Day 225 (Wk 32)	Day 253 (Wk 36)	Day 281 (Wk 40)	Day 309 (Wk 44)	Day 337 (Wk 48)	Day 365 (Wk 52)/ End of Treatment	Notes
Study Drug									
Contact IVRS/IWRS	X	X	X	X	X	X	X		
Dispense diary cards	X	X	X	X	X	X	X		
Collect and review diary cards		X	X	X	X	X	X	X	
Dosing of weekly abatacept	X	X	X	X	X	X	X		Must be administered weekly between visits. See Section 4.5 No dose administered at the End of Treatment visit
Dispense monthly abatacept kits	X	X	X	X	X	X	X		
Reconciliation of abatacept monthly kits		X	X	X	X	X	X	X	

^a All visits and procedures during the Open-label Treatment Period must occur within ± 3 days of the expected visit

^b Same Day as Double-Blind Day 169

^c Procedure to be performed by an ophthalmologist experienced in the diagnosis and treatment of Sjögren’s syndrome patients. Eye assessments must be performed within ± 5 days of the study visit.

Table 5.1-6: Follow-Up Period Procedural Outline for IM101603 (After Last Dose of Study Medication)^a

Procedure	28 Days	84 Days	Notes
Adverse Events Assessment	X	X	
Laboratory Tests			
Urine/Serum Pregnancy	X	X	
Serum anti-abatacept antibodies	X	X	
Pharmacokinetic (PK) Sampling ^b	X	X	

^a These visits should occur 28 and 84 days after the last dose of study medication. If study medication is discontinued during the Double-Blind Treatment Period and the subject continues to be followed for the scheduled Double-Blind Treatment Period visits these additional visits may not be required.

^b The samples for PK will be evaluated to determine serum abatacept concentration in the event there is a corresponding positive immunogenicity result

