At the end of the double blind treatment period there will be a 197 day open label extension (OLE). On Day 169 all subjects continuing on treatment (including those subjects who received placebo during the double blind period) will receive open-label abatacept SC, 125mg weekly to Day 357. Subjects not wishing to continue on open-label abatacept have the option of discontinuing treatment at the end of the Double-Blind Period and proceeding to the post-treatment follow-up period. Study procedures will occur as specified in protocol Table 5.1-3.

Follow-Up Period:

Subjects who discontinue treatment of study drug during the double-blind or open-label periods or complete the study will have three follow-up visits 28, 85 and 169 days after the last treatment visit, to perform safety and laboratory assessments, including immunogenicity testing. Subjects who go into the post-study drug access program (i.e. switch from study drug to post-study abatacept) will be excluded from the Follow-up period.

The study design schematic is presented in Figure 2.1-1. On office visit days, SC injections should occur after all assessments (including efficacy, AE, blood draws for assessment of immunogenicity and drug concentrations) are done.

Figure 2.1-1: Study Design Schematic

The approximate duration of the study is up to a 4-week screening period (28 days), a 24-week Double-Blind Period (169 days), a 197-day open label abatacept period and a subsequent 24 week follow up period (169 days), for a total of approximately 80 weeks (561 days).

The start of the trial is defined as the date the first subject signs the informed consent. End of trial is defined as the last visit or scheduled procedure shown in the Time & Events schedule for the last subject. The study will continue beyond primary endpoint collection until the End of Trial.

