The continuous primary, secondary and exploratory endpoints in the list given above will be analyzed using the longitudinal repeated measures model given in [Section 7.1](#). For the non-key secondary and exploratory endpoints, the stratification variable by day interactions will be removed from the model (the baseline variable and baseline-by -day interaction will be kept). All timepoints of the Double-Blind Treatment Period and the open-label period (at which endpoint is collected) will be included. The treatment variable in the model is the original randomized treatment. This analysis will include all efficacy measurements collected up to last dose +42. The baseline measurement in the model will correspond to the variable that is analyzed. The modified ITT population will be used. In addition, some of these endpoints (see [Section 4.2](#) and [4.3](#)) will also be analyzed for the following 2 subgroups:

- subgroup of subjects with stimulated whole salivary flow of at least 0.1mL/min at both screening and baseline
- subgroup of subjects with stimulated whole salivary flow of less than 0.1mL/min at screening or baseline.

The subgroup analyses mentioned in the 2 bullets above will only be provided if there are at least 10 subjects in each treatment group in each of the subgroups

The longitudinal repeated measures model for these subgroup analyses will not include the stimulated salivary flow stratification variable. At each timepoints the adjusted changes for the 2 treatments will be provided. No treatment differences will be provided for the open-label timepoints.

Plots of the adjusted mean changes (95%) over time (from Day 29 up to Day 365) per treatment group will be provided for the primary and key secondary endpoints.

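### SAP Table 8.5-1 has no Day 337 (Week 48) window and gives Day 365 (Week 52) the range 324–351, so Week 48 values are dropped or reported as Week 52

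*SAP*

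**What the plan says.** Protocol Table 5.1-3 schedules open-label visits at Day 309 (Week 44), Day 337 (Week 48) and Day 365 (Week 52). ESSDAI, ESSPRI, joint counts, both global assessments, PROMIS Fatigue, the two dryness scales and ESR are marked at all three. Footnote a sets the tolerance: "All visits and procedures during the Open-label Treatment Period must occur within ± 3 days of the expected visit".

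SAP Section 8.5 assigns each measurement by its day relative to first dose, not by the visit named on the CRF. Where a window holds more than one measurement, "the measurement closest to the target day will be used". In the first assessment column of Table 8.5-1 (vital signs, routine laboratory tests and the monthly efficacy measures), the last two open-label rows are:

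| Row label | Target day | Range |
|---|---|---|
| Day 309 (Week 48) | 309 | 296–323 |
| Day 365 (Week 52/ET) | 365 | 324–351, footnote c |

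Footnote c reads: "The upper limit of the last visit window is 42/56 (efficacy/safety) days post the last study drug dose during the open-label period". SAP Section 2.1 says that subjects continuing on treatment "will receive open-label abatacept SC, 125mg weekly to Day 357".

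For the analysis from Day 1 to Day 365, SAP Section 7.5.2.1 states: "All timepoints of the Double-Blind Treatment Period and the open-label period (at which endpoint is collected) will be included".

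**The concern.** Day 365 lies outside the range printed for it, and a visit at which most efficacy measures are collected has no row. Because study day governs, the CRF visit label cannot repair this. Three things follow.

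- The Year 1 repeated-measures analyses cannot include Week 48 as a time point, although Section 7.5.2.1 calls for every open-label time point at which the endpoint is collected.
- Section 7.5.2.2 counts missing responses as non-response at each time point to Day 365. A subject who responded at Day 337 and has no later visit would be counted as a Week 52 responder, which bypasses that rule.
- Plots and by-visit tables would show Week 44 data under a Week 48 label.

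Two programmers could also build different Week 52 datasets from the same text, depending on whether they take 351 or footnote c as the limit.

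**Working it through.** **Inputs.** Targets and ranges: SAP Table 8.5-1, first assessment column. Visit days and ±3-day tolerance: Protocol Table 5.1-3. Last planned open-label dose, Day 357: SAP Section 2.1 and Protocol Section 3.1.3.

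**Step 1: week labels.** Week = (day − 1)/7.
- Day 309: 308/7 = 44, but the SAP prints Week 48.
- Day 337: 336/7 = 48. No SAP row.
- Day 365: 364/7 = 52, as printed.

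**Step 2: the table's own window rule.** In all ten rows from Day 57 to Day 309 the range is target − 13 to target + 14. For example, Day 281 gives 268–295 and Day 309 gives 296–323, both as printed. (Day 29 has the same upper offset but starts at Day 2, straight after the Day 1 window.) Continuing the rule:
- Day 337: 337 − 13 = 324 and 337 + 14 = 351, exactly the range printed against Day 365.
- Day 365: 365 − 13 = 352 and 365 + 14 = 379, before footnote c.

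The printed offsets for Day 365 are 324 − 365 = −41 and 351 − 365 = −14, so the Week 48 range stands in the Week 52 row. The other footnoted post-baseline ranges in Tables 8.5-1 and 8.5-2 whose target is Day 169 or Day 365 (156–183, 128–212 and 128–267 for Day 169; 309–421 and 268–421 for Day 365) all contain their targets.

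**Step 3: printed range taken alone.** With tolerance, Day 337 falls on 334–340 and Day 365 on 362–368. The first is inside 324–351. The second is outside by 362 − 351 = 11 to 368 − 351 = 17 days. The Week 48 value would be reported as Week 52, and the real Week 52 value would have no window.

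**Step 4: footnote c applied.** With the last dose on Day 357, the upper limit is 357 + 42 = 399 for efficacy and 357 + 56 = 413 for safety. The lower limit stays at 324.

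| Visit | In 324–399? | Distance to target 365 |
|---|---|---|
| Day 337 | yes | 28 days |
| Day 365 | yes | 0 days |

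If both visits exist, Day 365 is kept and Day 337 is dropped. If only Day 337 exists, it becomes the Week 52 value. The safety limit gives the same result.

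**Step 5: extent.** After Day 169 the protocol has seven open-label visits (Days 197, 225, 253, 281, 309, 337 and 365), and one loses its window. The second assessment column (SF-36, FSFI, salivary flow, eye tests) is not affected: its range of 309–421 contains Day 365, and Table 5.1-3 schedules none of those measures at Day 337.

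**The case against.** The strongest objection is that a table row may have been lost when the PDF was read. A stray Week 48 label beside a stray 324–351 range is what a merged row could leave, and other tables in this SAP text are visibly damaged. This cannot be excluded without the source file. Against it, both rows have all their cells, the windows run on without a gap, and the footnote c marker, which belongs to the last window, sits on 324–351.

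Second, footnote c is clearly meant to set the operative limit, so the 11-to-17-day miss is the less likely reading. That is right for subjects dosed to Day 357. But the footnote leaves the lower limit at 324, so the shared window remains.

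Third, the row is labelled as also covering early termination, so capturing some early values may be intended. That could explain a wide window. It does not explain leaving a scheduled visit without one.

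Fourth, the protocol text supplied shows history only to Amendment 01, while the SAP lists later amendments. Its summary of them mentions no removal of the Day 337 visit, and Day 365 lies outside 324–351 whatever the schedule.

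Fifth, the effect on safety output is narrow. Adverse events and marked laboratory abnormalities are selected by date relative to dosing, not by these windows. The routine laboratory rows of Table 5.1-3 are not visible, so collection at Day 337 is unconfirmed. Vital signs are recorded at every office visit (Protocol Section 5.3.5) and are affected. These limits narrow the point but do not remove it.

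**Conclusion.** The concern holds. On the operative reading with footnote c, Week 48 has no window: its values are discarded for subjects who also have a Week 52 visit and are reported as Week 52, 28 days early, for those who do not. On the printed range alone, on-schedule Week 52 values fall outside their window. Week 44 is mislabelled on either reading.

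The effect is confined to the open-label part of the Year 1 report, for measures in the first assessment column. Section 7.5.2.1 adds that "No treatment differences will be provided for the open-label timepoints", so no between-arm comparison is at risk. The Day 169 primary and key secondary analyses use other windows (156–183 and 128–212) and do not change.

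This assumes that the table is printed in the SAP as it appears in the text, that the Day 337 visit was retained in the later protocol amendments, and that dosing runs to Day 357. The number of subjects with a Day 337 value but no Day 365 value cannot be known from the documents.

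**What to change.** Check the table against the source SAP to rule out a lost row. If it stands as read, correct the first assessment column of Table 8.5-1:

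| Visit | Target day | Range |
|---|---|---|
| Day 309 (Week 44) | 309 | 296–323 |
| Day 337 (Week 48) | 337 | 324–351 |
| Day 365 (Week 52/ET) | 365 | 352 to the footnote c limit |

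Each scheduled visit, with its ±3 days, then falls in its own window (334–340 and 362–368). The second assessment column needs no change.

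The cost is one corrected label, one added row, one changed lower limit, and the matching edit to the visit-window program and output shells, made before the Year 1 analysis. Data collection and the Day 169 analyses are untouched.
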